15. INTERIM ANALYSIS

An interim analysis has not been planned for this study.

16. DETAILS ON DATA HANDLING

16.1 Baseline definition

Unless otherwise specified, baseline is defined as the values collected during the baseline visit, which is to occur during the in-center training. If multiple values are available, the value closest to the start of treatment will be used for baseline.

If a patient had re-enrolled and collected separate baseline data for their latter enrollments, then the baseline value collected with each corresponding enrollment should be used as baseline. For example, if patient X enrolled once under X.1 and again under X.2 and collected baseline data for both, then all data associated with X.1 should use the values collected at baseline for X.1, and those data associated with X.2 should use the values collected at baseline for X.2. If a patient re-enrolled and did not re-collect baseline values, then the data taken at their first baseline visit will be counted as baseline. If baseline data is missing, then data from screening may be used as baseline.

For Total KT/V_{urea} , if a value is available within 45 days of screening, then this value will serve as the baseline. If a value is not available, a new value will be taken during the screening period to use as baseline.

Any medical condition that is present at the time that a participant is screened will be considered baseline medical history and is not reported as an adverse event.

16.2 Handling of Missing or Incomplete Dates/Times

Unless otherwise specified, missing dates and times will not be imputed.

16.2.1 Treatment Start and Stop Dates

No imputation will be done if the treatment start/stop dates are missing.

16.2.2 Concomitant Medication Start and Stop Dates

If medication start date is unknown but the stop date is prior to the start of the study treatment, then the medication will be classified as “Prior”. If medication start date is unknown and stop date is also unknown, then the medication will be classified as “Concurrent”.

16.2.3 Adverse Event Start and Stop Dates

If the start date/time of an adverse event is missing and the stop date/time is prior to the date of first treatment, then the adverse event will be classified as a pre-treatment adverse event. If the start date/time is missing and the stop date/time is either missing or after the date of first treatment, then the adverse event will be classified as treatment-emergent.

Start and stop dates for adverse events will not be imputed.

16.3 Visit Windows/Unscheduled Visits

The visit windows are defined below:

Table 1: Visit Windows

Time-point/Visit	Time Window
Screening	Approximately 3 weeks
Baseline period	Approximately 2 weeks after Screening
Simulated Treatment (Visit 1)	Up to 7 days prior to Day 1 of Study Treatment period
Visit 2	Any time during week 4 of treatment
Total Kt/V_{urea} visit	Any time between week 5 thru 8 of study treatment
Visit 3	Any time during week 8 of study treatment
Visit 4	Any time during week 12 of study treatment
End of Study Visit or Early Termination visit	5 days after last treatment with AMIA APD Solution Generation System

In the instance that multiple results are collected at the baseline visit, the last available result will be used in the analyses. For assessments collected post-baseline, the first available result will be used, or the assessment from the withdrawal visit will be used if the nominal visit result is unavailable. All re-tests will be presented in safety listings.

Results from unscheduled visits will not be included in the table summaries. These values will only be presented in the listings.

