### **6.8 Removal of Patients from the Study**

Patients are considered withdrawn / prematurely discontinued from the study if their participation is stopped before completion of the required evaluations as described in this protocol (see Section 3.5.1). If a patient is prematurely removed from the study, all data prior to discontinuation should be recorded in the eCRF and all available data will be included in all analyses.

The Investigator may terminate a patient's study participation at any time during the study if he/ she judges it to be in the patient's best interest. If a patient is withdrawn from the study, the Clinical Study Manager or Monitors should be informed at the earliest possible opportunity, regardless of the reason(s) for withdrawal. In addition, a patient may discontinue his or her participation at any time during the study without having to justify the decision. If a patient's participation is discontinued, the reason(s) must be recorded in the source documents and on the eCRF. If a patient discontinues for any reason, every effort should be made to perform all of the procedures that are scheduled for the End-of-Study/ Early Termination Visit. In addition, SAEs, related or not and ADEs, will be followed post-study according to the safety plan.

---

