### **8.9 Follow-up Period**

After the last study treatment with AMIA APD Solution Generation System, patients will transition back to Standard AMIA treatment with Baxter's approved Dianeal Low Calcium (2.5 mEq/L) PD Solution and enter a Follow-up Period of 5-10 days. During this time, an assessment by an Investigator or a designee will occur. At a minimum, this assessment will include evaluation of BP, pulse rate, weight, fluid status and dialysis prescription. Adverse events, SAEs, ADEs and SADEs will be collected throughout the Follow-up Period and through the End-of-Study/ Early Termination Visit.

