### **8.10 End of Study Visit or Early Termination Procedures**

The End of Study assessments will be performed 5-10 days after the last treatment with the AMIA APD Solution Generation System (i.e., at week 13 for patients who completed the 12 weeks of treatment). If a patient discontinues from the study prematurely, every attempt should be made to perform all procedures and evaluations that are scheduled for the End of Study/ Early Termination Visit. A patient who withdraws from the study after installation and after meeting all the inclusion criteria and none of the exclusion criteria is considered an Early Termination patient. In addition, a patient who withdraws from the study after installation but before confirming that all the inclusion criteria and none of exclusion criteria are met and withdraws due to a device-related issue (e.g., leaking, alarms, etc.), is also considered an Early Termination patient.

The following data will be collected:

1. Collection of AEs/ SAEs.
  2. Adverse events of special interest (Refer to Section [7.2.1](#) for the full list of AESIs).
  3. Physical examination including weight.
  4. Assessment by an Investigator or a designee.
  5. Vital Signs.
- 
- 

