## **10. PLANNED STATISTICAL METHODS**

### **10.1 General Considerations**

Further details of the planned statistical methods will be provided in the study SAP. The SAP will be finalized prior to database lock. Any changes to the statistical methods described in the protocol will be documented in the SAP.

Unless otherwise noted, all analyses will be performed using SAS/GRAPH® 9.4 software, SAS/STAT® 14.1 software and Base SAS® 9.4. Copyright© 2002-2012, SAS Institute Inc. SAS and all other SAS Institute Inc. product or service names are registered trademarks or trademarks of SAS Institute Inc., Cary, NC, USA. All Rights Reserved.

Summary statistics will be presented with mean, standard deviation, median, minimum and maximum for continuous variables and frequency count and percentage based on study population will be used to summarize categorical variables. Prior to analysis, data will be reviewed for consistency. Missing data values will not be imputed and all non-missing values will be used. To determine patients who had been re-enrolled in the study, there will be a question on the eCRF indicating whether the patient has been enrolled in the trial previously and the number the patient was previously enrolled under. The details on how data from these patients will be analyzed will be described in the SAP.

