12. CHANGES IN PLANNED ANALYSES FROM THE PROTOCOL

There have been no changes from the planned analyses in the protocol.

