- ⁱ Medication history will include all medications that are still active, taken within the 30 days prior to Screening, with each medication having a corresponding indication recorded in the Medication and Medical History eCRFs.
- ^j Vital signs (BP and pulse rate) will be recorded on the eCRF at Screening, Study Visit 2, Study Visit 3, Study Visit 4, and at the End-of-Study Visit. Weight will be recorded at Screening and at the End-of-Study Visit. Blood pressure will be measured with an appropriate cuff size after the patient has been sitting for at least 5 minutes.
- ^k Please refer to the Point of Care APD Clinic and Home Assessment Guide for the procedures involved in the home suitability assessment.⁹
- ^l The Principal Investigator or a designee (e.g., sub-investigator) will assess each patient at the Screening Visit and on a weekly basis. At a minimum, this assessment will include evaluation of BP, pulse rate, weight, fluid status and dialysis prescription.
- ^m AEs and SAEs will be collected after the informed consent is signed and will continue to be collected throughout the Study Treatment Period and during the follow-up period of 5-10 days after the last study treatment. Adverse device events and SADEs will be collected from the time of signing informed consent.
- ⁿ Medications taken during the study will be documented throughout the study and will include a review of all major body systems and renal history (primary etiology of renal disease and current PD prescription).
- ^o Patients will receive device-specific training which will last up to 2 weeks.
- ^p Comprehension and retention testing will occur at the end of the Baseline Period (In-center Training Period) for patients and care partners (if participating). If the patient does not read and understand English, the care partner will assist the patient with comprehension and retention testing.
- ^q The Investigator must reassess the stability of the patient during the Baseline Period (In-center Training Period). Once the clinician concludes that the patient is clinically stable and their PD prescription is stable, then the patient can begin treatment in the home.
-
- 

-
- ^r Written confirmation of independent care by patient and care partner (if participating).
- ^s Machine information will include the available code number(s) and a lot/serial number(s) at initial installation and if the device or any of the disposables are changed.

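### Read literally, SAP 16.3 lets an Early Termination vital-sign reading, taken off the study system, stand in for a missing Visit 2, 3 or 4 result; protocol 10.1 rules out imputation and SAP 12 declares no change

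*SAP*

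**What the plan says.** SAP 16.3 sets the rules for repeated and missing results. After baseline the first available result counts, and "the assessment from the withdrawal visit will be used if the nominal visit result is unavailable". No visit in SAP Table 1 is called a withdrawal visit. The natural match is the combined End of Study/Early Termination row.

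Vital signs are "recorded on the eCRF at Screening, Study Visit 2, Study Visit 3, Study Visit 4, and at the End-of-Study Visit" (SAP Appendix 1, footnote j; protocol 6.4 agrees). SAP 14.3.3 summarises them at each time-point, as values and as changes from baseline.

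On timing, protocol 8.10 says "The End of Study assessments will be performed 5-10 days after the last treatment with the AMIA APD Solution Generation System", while SAP Table 1 gives "5 days after last treatment with AMIA APD Solution Generation System". Protocol 8.9 says that after the last study treatment "patients will transition back to Standard AMIA treatment"; protocol 5.4 adds HomeChoice.

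On missing data, protocol 10.1 says "Missing data values will not be imputed and all non-missing values will be used" and requires changes of method to be documented in the SAP. SAP 12 says "There have been no changes from the planned analyses in the protocol". For patients removed early, protocol 6.8 says "all available data will be included in all analyses". SAP 7.3 files an additional, unscheduled termination visit under the termination visit. For a patient who does not return, it leaves the last assessments at the last visit attended.

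**The concern.** A rule that moves a reading from one visit into another visit's row because that row is empty is single-value substitution. Here the donor reading is also taken under different conditions. Visits 2 to 4 describe patients on the study system, whereas the termination reading is scheduled after the patient has left it. People who leave early may also differ from those who stay: the reasons in protocol 3.5.1 include adverse events and inadequate dialysis.

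Vital signs are a named secondary safety endpoint. In a single-arm descriptive study the tables are the result, so a Visit 4 row should contain Visit 4 readings. The SAP does not ask for substituted values to be flagged. A reader would have to trace them through the disposition and vital-sign listings.

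**Working it through.** **1. Which summaries the clause can reach.** A measure must be collected both at a nominal post-baseline visit and at termination, and be summarised by visit. From Appendix 1 and protocol 8.10:

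- Dialysis solution, product water and holding-bag samples: Visits 1 to 4, not termination. Not reached.
- Kt/V and clinical laboratory tests: Screening (or an earlier Kt/V value) and the Kt/V visit, not termination. Not reached.
- Feed water and weight on the eCRF: Screening and the end of the study, not Visits 2 to 4. Not reached.
- Vital signs: Visits 2, 3 and 4 and termination. Reached.

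**2. Whether the donor value is off-system.** Under either stated window, 5 days or 5-10 days, the visit falls at least 5 days after the last study-system treatment. By plan it is off-system.

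**3. How far one reading could travel under the literal text.** Take day 1 as the first treatment, with no interruptions. Week w covers days 7(w − 1) + 1 to 7w, so Visits 2, 3 and 4 fall on days 22-28, 50-56 and 78-84. A patient who stops on day 14 has a termination visit on days 14 + 5 = 19 to 14 + 10 = 24. If that reading fills later rows, it was taken:

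- 50 − 24 = 26 to 56 − 19 = 37 days before Visit 3;
- 78 − 24 = 54 to 84 − 19 = 65 days before Visit 4.

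**4. Share of substituted values at Visit 4.** The plan gives no dropout rate, so there is no figure to reproduce. Inputs: 30 completers (the target in protocol 10.2), all assumed to have a Visit 4 reading; N treated (assumed); k = N − 30 leavers, all missing Visit 4.

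| N treated | k | All leavers have a termination reading: k/N | Half do: 0.5k/(30 + 0.5k) |
|---|---|---|---|
| 31 | 1 | 1/31 = 3.2% | 0.5/30.5 = 1.6% |
| 35 | 5 | 5/35 = 14.3% | 2.5/32.5 = 7.7% |
| 40 | 10 | 10/40 = 25.0% | 5/35 = 14.3% |
| 50 | 20 | 20/50 = 40.0% | 10/40 = 25.0% |

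**5. Pattern over visits.** Assume one third of leavers go before Visit 2, one third between Visits 2 and 3, and one third between Visits 3 and 4, all with a termination reading.

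*Reuse allowed* (k/3, 2k/3 and k filled out of N):

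- N = 35: 4.8%, 9.5%, 14.3%
- N = 40: 8.3%, 16.7%, 25.0%

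*Only the next visit due is filled* (k/3 filled at each visit; denominators N, N − k/3 and N − 2k/3):

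- N = 35: 1.67/35 = 4.8%, 1.67/33.33 = 5.0%, 1.67/31.67 = 5.3%
- N = 40: 3.33/40 = 8.3%, 3.33/36.67 = 9.1%, 3.33/33.33 = 10.0%

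**6. Effect on a mean.** The shift equals the share times the difference d between substituted and on-system readings. The documents give no d. With d of 3, 5 or 10 mmHg (purely illustrative), the Visit 4 mean moves by 0.43, 0.71 or 1.43 mmHg at 5 leavers, and by 0.75, 1.25 or 2.5 mmHg at 10.

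**The case against.** The strongest reply is that the clause is unclear rather than wrong. It speaks of a nominal visit result in the singular and names neither vital signs nor Visits 2 to 4. It might only let a leaver's assessment serve as the End of Study result, or fill only the visit missed at withdrawal. SAP 7.3 supports restraint, since both of its sentences keep values at the visit where they were collected. These readings are possible, but 16.3 does not state them, and 7.3 governs recording without overriding 16.3. What stands is that reuse across three visits, and a mix that grows with time, are permitted by the text and not certain. Even the one-visit reading puts an off-system value in an on-system row.

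A second reply is that protocols 10.1 and 6.8 want all available data used, and that assigning one observed value to one visit is visit mapping. Table 1 already sets the visit windows, however, and this clause acts only when no nominal result exists. A row for the termination visit uses the data without relabelling them. It is true that the conflict with 10.1 is plainest if one value is reused. It is also true that 14.3.3, by summarising each time-point, already implies such a row.

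A third reply is that little is at stake: no test, no threshold, and a solution formulated to be nominally equivalent to Dianeal Low Calcium. That stands, and it limits the weight of the point.

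A reader might infer a direct contradiction between 16.3 and 7.3, because 16.3 keeps unscheduled-visit results out of the tables. The documents support only an ambiguity: it is not settled whether a termination visit held as an unscheduled visit can supply a substitute.

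**Conclusion.** The point holds as a defect of wording with a limited reach. As written, SAP 16.3 permits an off-system Early Termination reading to replace a missing Visit 2, 3 or 4 vital-sign result. That is at odds with protocol 10.1, sits poorly with SAP 7.3, and is not declared in SAP 12.

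Two stronger conclusions are tempting and not supported. One is that the primary endpoints or Kt/V are contaminated; the schedule rules that out. The other is that 40% of Visit 4 values would be substituted. That figure needs all 50 patients to be treated and all 20 leavers to have a termination reading. Fifty is an enrolment cap, SAP 7.1 defines enrolled by installation and eligibility rather than treatment, and protocol 5.2 lets the sponsor stop enrolment early. All the shares are upper bounds or scenarios on assumed numbers treated, and the size and direction of any bias are unknown.

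Two neighbouring points are separate and add no weight. Protocol 10.6 plans a pre-to-post treatment change in vital signs, most naturally from the readings before and after treatment in protocol 8.5. SAP 14.3.3 gives change from baseline only, Appendix 1 has no vital-sign mark under Each Treatment Day, and SAP 12 is silent. The End of Study/Early Termination window also differs between SAP Table 1 and protocol 8.10.

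**What to change.** Delete the substitution clause from SAP 16.3. Suggested text: *For post-baseline assessments, the first result at the nominal visit is used. Early Termination vital signs are summarised in a separate row and do not replace a missing Visit 2, 3 or 4 result.* State whether a termination visit held as an additional, unscheduled visit counts towards that row.

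The cost is SAP wording and table code; no new data are needed. Later rows will show a smaller n. In the scenarios above, Visit 4 would rest on 30 patients instead of up to 35, 40 or 50.

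Separately, reconcile protocol 8.5 and 10.6 with 6.4 and Appendix 1. Then produce the pre-to-post summary if the readings were captured, or record its removal in SAP 12. Reconcile the SAP Table 1 window with protocol 8.10.

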16.4 Pooling Strategy for Study Sites

Data will be pooled across all study sites.

17. LIST OF TABLES, FIGURES AND LISTINGS

Table Number	Table Name
14.1.1	Patient Overview
14.1.2	Patient Disposition
14.1.3	Protocol Deviations Summary
14.1.4	Categorical Demographic and Baseline Characteristics
14.1.5	Continuous Demographic and Baseline Characteristics
14.2.1	Overall Testing of the Chemical Composition of the Dialysis Solution (Primary Efficacy Endpoint)
14.2.2	Individual Parameter Testing of the Chemical Composition of the Dialysis Solution
14.2.3	Individual Parameter Summary of the Chemical Composition of the Dialysis Solution
14.2.4	Total Kt/V _{urea} Summary (Secondary Efficacy Endpoint)
14.2.5.1	eDiary Treatment Summary
14.2.5.2	Treatment Interruptions Summary
14.3.1.1.1	Summary of Adverse Events
14.3.1.1.2	Treatment-Emergent Adverse Events by SOC and Preferred Term
14.3.1.1.3	Serious Treatment-Emergent Adverse Events by SOC and Preferred Term
14.3.1.1.4	Treatment-Emergent Adverse Events Related to Study Device by SOC and Preferred Term
14.3.1.1.5	Treatment-Emergent Adverse Events Related to Typical PD Therapy by SOC and Preferred Term
14.3.1.1.6	Treatment Emergent Adverse Events Related to Another Baxter Product by SOC and Preferred Term
14.3.1.1.7	Serious Treatment-Emergent Adverse Events Related to Study Device by SOC and Preferred Term
14.3.1.1.8	Serious Treatment-Emergent Adverse Events Related to Typical PD Therapy by SOC and Preferred Term
14.3.1.1.9	Serious Treatment-Emergent Adverse Events Related to Another Baxter Product by SOC and Preferred Term
14.3.1.1.10	Treatment-Emergent Adverse Events Leading to Withdrawal by SOC and Preferred Term
14.3.1.1.11	Treatment-Emergent Adverse Events Leading to Death by SOC and Preferred Term

14.3.1.1.12	Treatment-Emergent Adverse Events of Special Interest by SOC and Preferred Term
14.3.1.1.13	Treatment-Emergent Adverse Events in $\geq 5\%$ of Patients by SOC and Preferred Term
14.3.1.3.1	Treatment-Emergent Adverse Events by SOC, Preferred Term, and Severity
14.3.1.3.2	Treatment-Emergent Adverse Events by SOC, Preferred Term, and Relationship with Study Device
14.3.1.3.3	Treatment-Emergent Adverse Events by SOC, Preferred Term, and Relationship with Typical PD Therapy
14.3.1.3.4	Treatment-Emergent Adverse Events by SOC, Preferred Term, and Relationship with Another Baxter Product
14.3.4.1	Hematology Laboratory Summary at Baseline
14.3.4.2	Chemistry Laboratory Summary at Baseline
14.3.5.1	Vital Signs Summary and Change from Baseline
14.3.6.1	Summary of Device Deficiencies
14.3.6.2	Summary of Device Deficiency Characteristics
14.3.7.1	Microbiological and Chemical Testing of the Product Water from the Water Device (pre-sterilizing filter) (Primary Safety Endpoint)
14.3.7.2	Individual Parameter Microbiological and Chemical Testing of the Product Water from the Water Device (pre-sterilizing filter)
14.3.7.3	Individual Parameter Summary of Microbiological and Chemical Testing of the Product Water from the Water Device (pre-sterilizing filter)
14.3.7.4	Microbiological Testing of the Water from the Holding Bag (Primary Safety Endpoint)
14.3.7.5	Individual Parameter Microbiological Testing of the Water from the Holding Bag
14.3.7.6	Individual Parameter Summary of Microbiological Testing of the Water from the Holding Bag
14.3.7.7	Testing of the Feed Water
14.3.7.8	Individual Parameter Testing of the Feed Water
14.3.7.9	Individual Parameter Summary of Feed Water
Listing Number	Listing Name
16.2.1	Patient Disposition
16.2.2	Protocol Deviations
16.2.3	Patient Overview
16.2.4.1	Demographic and Baseline Characteristics
16.2.4.2	Concomitant Medications by Coded Drug Term
16.2.4.3	Non-Drug Therapies by Coded Term

16.2.4.4	Medical History
16.2.4.5	Renal Medical History
16.2.4.6	In-Center Training Log
16.2.6.1	Chemical Composition of Dialysis Solution
16.2.6.2	Total Kt/V _{urea} Measurements
16.2.6.3	eDiary Treatment Information
16.2.6.4	Treatment Interruptions Information
16.2.7.1.1	Treatment-Emergent Adverse Events
16.2.7.1.2	Pre-Treatment Adverse Events
16.2.7.1.3	Treatment-Emergent Adverse Events Leading to Withdrawal
16.2.7.1.4	Treatment-Emergent Adverse Events Leading to Death
16.2.7.1.5	Treatment-Emergent Adverse Events Related to Study Device
16.2.7.1.6	Treatment-Emergent Adverse Events Related to Typical PD Therapy
16.2.7.1.7	Treatment-Emergent Adverse Events Related to Another Baxter Product
16.2.7.1.8	Treatment-Emergent Adverse Events of Special Interest
16.2.7.1.9	Serious Treatment-Emergent Adverse Events
16.2.7.1.10	Serious Pre-Treatment Adverse Events
16.2.7.1.11	Serious Treatment-Emergent Adverse Events Leading to Withdrawal
16.2.7.1.12	Serious Treatment-Emergent Adverse Events Leading to Death
16.2.7.1.13	Serious Treatment-Emergent Adverse Events Related to Study Device
16.2.7.1.14	Serious Treatment-Emergent Adverse Events Related to Typical PD Therapy
16.2.7.1.15	Serious Treatment-Emergent Adverse Events Related to Another Baxter Product
16.2.7.1.16	Treatment-Emergent Suspected Unexpected Serious Adverse Reactions or Unexpected Adverse Device Effects
16.2.7.2	Patient Deaths
16.2.8.1	Laboratory Measurements
16.2.8.2	Abnormal Laboratory Measurements
16.2.9.1	Vital Signs
16.2.11.1	Microbiological and Chemical Contamination Testing of the Product Water from the Water Device (Pre-Sterilizing Filter)
16.2.11.2	Microbiological Testing of the Water from the Holding Bag
16.2.11.3	Testing of the Feed Water
16.2.12.1	Device Deficiencies and Product Issues

16.2.12.2	Device Deficiencies Resulting in an Alarm
16.2.12.3	Device Deficiencies Leading to AEs
16.2.12.4	Device Deficiencies Leading to SUSARs
16.2.12.5	Device Deficiencies Leading to UADEs

